8.1.1 Prohibited Therapy

The following rules concerning concurrent treatment(s) will apply in this study:

- Participants may not receive other investigational drugs during the period of study participation.
- Participants may not be switched to an ART regimen containing maraviroc and/or enfuvirtide.
- The use of other immune-suppressive agents is prohibited, unless they are being used to treat an AE.
- Restrictions on medications taken prior to enrollment in the study are described in **Section 5.2**.
- Vaccinations, inclusive of flu vaccines, prohibited within 4 days prior to Day 0 through 5 days after last infusion of study drug.
- Participants requiring any systemic antiviral, antifungal, or antibacterial therapy for active infection must have completed treatment no less than one week prior to initiation of study drug.

8.1.2 Permitted Therapies

Participants may receive the following concurrent therapy:

- Regularly prescribed medications such as antipyretics, analgesics, antidepressants, sleep medications, megestrol acetate, testosterone, and other medications for chronic conditions that do not interact with MGD014;
- Oral and topical antibiotics for bacterial infections;
- Intermittent use of inhaled corticosteroids (e.g., for chronic obstructive pulmonary disease [COPD], asthma) is only permitted for participants not receiving ritonavir or cobicistat as part of their current ART regimen and after consultation with the study PI or designee).

- Sporadic topical use of corticosteroids (e.g., creams) to small areas of the skin (15 cm^2) after consultation with the PI (or designee) is only permitted for participants who are not receiving ritonavir or cobicistat as part of their current ART regimen; and
- For treatment of IRR (Grade 1 and Grade 2) flu-like symptoms, non-steroidal anti-inflammatory drugs (NSAIDs) may be used to alleviate symptoms under a physician's guidance and for a limited period of time.

9 STUDY PROCEDURES

This section provides a general description of the procedures and assessments associated with this study. The timing of the study procedures is presented in [Appendix 1](#).

9.1 Study Visits

During the COVID-19 pandemic, alternative methods for conducting study assessments should be considered when compliance, feasibility, and safety can be assured. These methods may include:

- Remote visits, e.g., via telephone/video (using compliant video-conference tools as permitted by HIPAA regulations)
- Use of primary care centers and local laboratories for blood draws and imaging/radiographs

If alternative methods are used, local laboratory reference ranges will be documented and submitted to the sponsor. If local laboratory testing other than McLendon or LabCorp are used, their results and laboratory accreditation should be retrieved and documented in the participant's study records.

9.2 Informed Consent

Prior to performing any study-related procedure or assessments, the study coordinator discusses the study with the potential participant and obtains signed informed consent. This communication will be documented. Labs/procedures completed during a routine clinical care appointment that are the same as the study screening labs and/or procedures and completed within the 14 days preceding the screening visit can be used to qualify the participant upon approval by the study PI or designee.

9.3 Screening Period

Screening evaluations will be performed within 8 weeks (56 days) prior to study drug administration on Day 0 unless otherwise specified. At the 1st screening visit, participants will screen for the study. Only those participants who meet all eligibility criteria specified in [Section 5.1](#) Inclusion Criteria and [Section 5.2](#) Exclusion Criteria will be enrolled. A unique PID will be assigned during the screening visit. Participants who had previously completed Part 1 and are being considered for Part 2 will maintain the same PID and will be assigned a new study-specific identifier (SID).

Participants who are unable to meet protocol defined eligibility criteria at the Screening Visit (Step 1, Visit 1) may be eligible to re-screen again at the PI (or designee)'s discretion. In such cases, the same PID will be used. If a screen failure or the failure to enroll is due to the inability to meet one of the laboratory parameters (hematology, chemistry, HIV RNA, or CD4 T cell count), a laboratory retest of the failed criteria may be performed one time only. If the repeat value is within eligibility requirements, the participant can enroll on the study.

9.4 Enrollment and Registration

Step 1 Visit 1 determines eligibility and enrollment at Visit 2. Once the potential participant has been determined to be eligible for enrollment into the study, the participant must be registered with MacroGenics. The following information should be provided during registration:

- Year of birth
- Date of signed informed consent
- Planned date of first administration

Instructions for the registration process are provided in the Study SOP.

9.5 Medical History

Significant medical history should be obtained during the screening visit. All concurrent medical conditions in the last 60 days and any significant medical conditions (e.g., hospitalizations, surgeries, prior medical history) should be collected. Medical history obtained at Screening will include demographic information (e.g., date of birth, gender, race, and ethnicity, etc.), participant's medical history, HIV testing history (CD4 and VL) and HIV medication history, inclusive of prior genotypes (if available). Safety updates will occur at all clinical visits, according to [Appendix 1](#).

During the Step 1 screening period (prior to MGD014 administration), any untoward event that occurs should be collected as a concurrent medical history and not as an AE, unless it is due to a protocol-related procedure. Thereafter (i.e., after the time of study drug administration), any untoward event should be collected as an AE.

9.6 Prior and Concomitant Medications

All concomitant medications administered during screening and the participant's participation in the study until the end of study visit must be recorded in the source. Concomitant medications will be reviewed at every study visit.

Prescription and non-prescription medications taken within 4 weeks prior to screening must be recorded on the source document.

9.7 ART Adherence

ART adherence will be reviewed at every visit. Non-adherence will be defined as having missed more than 9 total days in the 3 months prior to screening. Assess any missed doses while on study and discuss with PI (or designee). Continuance on study will be contingent on ART adherence.

9.8 Physical Examination

Complete physical examination will include examination of skin, head, eyes, ears, nose, throat, lymph nodes, heart, chest, lungs, abdomen, extremities, and neurologic system according to schedule specified in [Appendix 1](#). A directed physical exam will be performed at the visits indicated in the SOE, according to [Appendix 1](#), and includes VS. The targeted or directed physical exam addresses any previously identified or new event that the participant experiences since the last study visit or any unresolved signs or symptoms previously experienced. In addition to the VS, this assessment includes updates to signs and symptoms, and clinical assessment of HIV disease.

9.9 Vital Signs

At each study visit, the VS (body temperature (T), pulse (P), respiratory rate (RR), seated blood pressure (BP)) and weight will be recorded according to the schedule specified in [Appendix 1](#). Height is only required at Step 1, Visit 1.

Repeat VS (T, P, RR, BP) may also be captured as necessary to elucidate the course of any untoward event or AE and may be inclusive of all or individual VS components as required to address monitoring of the AE.

9.10 Leukapheresis

Part 1:

The leukapheresis is optional in Part 1. Participants consenting to this optional procedure will have the procedure at Visit 2 or at any time point between Visit 2 and the day of the infusion.

Part 2:

The leukapheresis is optional in Part 2. Participants consenting to this optional procedure will undergo 2 leukapheresis procedures in Part 2. The first leukapheresis occurs at baseline completed at Visit 2. The second leukapheresis procedure will occur in Step 3, the post treatment phase, approximately 2 weeks post-completion of MGD014 therapy (\pm 2 weeks).

All leukapheresis products will be transported on the day of collection to the [REDACTED] Laboratory on the UNC campus.

NOTE: Refer to the Apheresis SOP and Study Specific Lab Manual for procedures specific to this study.

Participants who experience a Grade 3 or higher toxicity during the leukapheresis will be evaluated on a case by case basis to understand the cause of the Grade 3 event. If the clinical situations (i.e., vaso-vagal response) that lead to the discontinuation of the leukapheresis procedure is determined by the study PI in collaboration with the apheresis medical director to be situational and poses no apparent harm to the participant, the leukapheresis procedure may be repeated. However, if determined by the study PI, apheresis medical director, or the medical monitor that repeated leukapheresis would be harmful to the participant, then he/she will be terminated from the study.

The only exception to this discontinuation policy will be related to elevations in BP. Elevated BP observed during the leukapheresis procedure will be monitored via apheresis Lab policies. These will be noted and documented but will not be used to discontinue study participation.

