Step 3 Post-treatment Phase: This phase begins following the Day 28 MGD014 infusion and includes the 14 days between Day 28 and Day 42, with the first post-treatment study visit at Day 42. Step 3 is conducted over a 6-week period. During Step 3, if a baseline leukapheresis was performed, a second and final leukapheresis procedure is completed 2 weeks (+/- 2 weeks) following the final MGD014 infusion, for assessment of potential reduction in the frequency of resting CD4 T cell infection by QVOA. Plasma HIV-1 RNA as measured by SCA may be assessed. Serial blood draws will be obtained to determine PK and PD measures, and impact on T cell function.

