4.5 Study Duration and End of Trial

For each participant, the study duration will be approximately either 13 weeks (Part 1), or 19 weeks (Part 2). This includes a post treatment period of 6 weeks following the final MGD014 infusion through end of study, which is approximately 5 times the anticipated 8-day half-life based on preclinical animal studies. As participant accrual will be staggered so that the full 2-week DLT period will occur prior to dose escalation in Part 1, the overall study duration will be approximately 36 months. The end of trial is the date that all participants enrolled have completed their end of study visit. The end of trial is when the clinical study database is locked after the last participant in the study completes discharge procedures at the last visit and the study forms have been entered, monitored, reviewed, and approved by PI.

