5.3 Guidelines for Discontinuation of Participants from Study Drug Administration

Under certain circumstances, an individual participant's infusions will be prematurely or permanently discontinued. Specific events that will result in stopping a participant's infusion schedule in either Part 1 or Part 2 of the study include:

- Failure to meet requirements established for safety assessment
- Pregnancy
- Development of a DLT at any time following MGD014 infusion
- Investigator discretion
- HIV RNA > 150 copies/mL on 2 consecutive determinations

If the PI (or designee) decides that a participant should be withdrawn from study treatment, the sponsor must be alerted within 24 hours. All participants who discontinue treatments should comply with protocol specified visits and follow-up as required by the protocol. The only exception to this requirement is when a participant withdraws consent for all study procedures or loses the ability to consent freely (i.e., is imprisoned or involuntarily incarcerated for the treatment of either a psychiatric or physical illness).

If a participant is withdrawn before completing the study, the reason for withdrawal must be documented appropriately in the study documents.

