12 ADVERSE EVENT REPORTING AND ASSESSMENT OF SAFETY

The safety assessment will be based on the evaluation of all AEs that occur from the time of initiation of administration of study drug through the End of Treatment Visit or 30 days after the last dose of study drug (whichever is later) and will be determined based on signs, symptoms, physical examination findings, and/or laboratory test results from enrolled participants, as appropriate.

If an AE occurs, the study coordinator, in collaboration with the PI, will evaluate the severity and seriousness of the AE and the relationship to the study drug, and will document the findings.

All adverse events will be graded according to the Division of AIDS Table for Grading the Severity of Adult and Pediatric Adverse Events, corrected Version 2.1, July 2017, which can be found on the DAIDS Regulatory Support Center Web site: <http://rsc.tech-res.com/clinical-research-sites/safety-reporting/daids-grading-tables>.

AEs reported between the time the potential participant signs the informed consent form (ICF) and the administration of the first dose of study drug will be captured as medical history unless the AEs are attributed to protocol-specified procedures that are not part of standard of care that occur during this time period, in which case the AEs will be collected on the Source Document Adverse Event Form. Protocol-related AEs and SAEs will be collected from the time the participant has consented to study participation.

SAEs considered related to study drug may be reported at any time, even after the participant's final treatment visit.

The reporting of laboratory abnormalities as both laboratory findings and AEs should be avoided. Laboratory abnormalities should not be reported as AEs unless any one of the following are met:

- Any criterion for an SAE is fulfilled
- The laboratory abnormality causes the participant to discontinue from the study treatment
- The laboratory abnormality causes the participant to interrupt the study treatment
- The laboratory abnormality causes the participant to modify the dose of study treatment
- The laboratory abnormality requires intervention
- The PI (or designee) determines the laboratory value as an abnormal change from baseline and is of clinical significance for that participant

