12.2 Adverse Event Collection and Documentation

12.2.1 All Adverse Events

Adverse Events (AEs) leading to discontinuation, potential autoimmune events, AEs of \geq Grade 3 severity, related adverse events, and lab abnormalities as well as safety concerns, will be communicated in a timely manner to the UNC IRB, MacroGenics, National Institute of Allergy and Infectious Diseases (NIAID), and FDA per the reporting requirements of each body/authority. The sponsor of this study is MacroGenics. The PI at UNC-CH will be responsible for reporting to MacroGenics, who in turn, will be responsible for reporting to NIAIDs, and FDA per the reporting requirements of each body/authority. AEs occurring after the participant undergoes early termination or completes the trial need not be reported unless the event is serious, and the PI believes that the event may have been caused by the study drug or a protocol procedure.

All participants who receive at least one dose of study drug will be considered evaluable for safety. AEs will be determined based on signs, symptoms, physical examination findings, and/or laboratory test results from enrolled participants as appropriate.

All AEs whether serious or non-serious, will be evaluated from the time a signed and dated ICF is obtained until 30 days following the last dose of study drug. AEs and SAEs reported between the time the participant signs the ICF and the administration of the first dose of study drug will be captured as concurrent medical history unless the events are attributed to protocol-specified procedures. AEs attributed to protocol-specified procedures will be recorded in the database and provided to the sponsor. Additionally, the IRE form will be completed and provided, as appropriate.

All AEs must be reported, regardless of seriousness, severity, or presumed relationship to study drug, must be recorded using medical terminology in the AE source document. AEs will be coded to the Preferred Term using the current version of MedDRA available at study initiation. All records will need to capture:

- The details of the duration, severity, and seriousness of each AE,
- The action taken with respect to the study drug(s),
- The PI attribution/causality assessment concerning the relationship of the AE to study therapy,
- The outcome of the event.

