12.2.3 Serious Adverse Events

All SAEs occurring during the study must be reported to MacroGenics and the UNC IRB per the MacroGenics and UNC IRB reporting requirements. A written report (IRE Form) will be faxed or emailed to MacroGenics within 24 hours. Additional information will be supplied as requested. All SAEs occurring during the study will be reported by MacroGenics to DAIDS following guidelines for expedited AE (EAE) reporting and to the FDA according to those regulatory bodies' guidelines.

After 30 days following the last dose of study drug administration only SAEs the PI (or designee) considers related to study drug or a protocol procedure, should be reported to the sponsor.

Information regarding SAEs will be transmitted to the sponsor using the IRE Form, which must be completed and signed by the PI from the study site and transmitted to the sponsor within 24 hours of the site becoming aware of the serious adverse event.

All Grade 3 or Grade 4 SAEs considered related to study drug must be followed until recovery to baseline or Grade 1 with the date of resolution recorded in the source documents. In addition, the investigator should report all reportable Grade 3 or Grade 4 SAEs to the IRB. Resolution of an

event is defined as the return to pre-treatment status or stabilization of the condition with the expectation that it will remain chronic.

All SAEs that have not resolved by the end of the study, or that have not resolved upon discontinuation of the participant's participation in the study, must be followed until any of the following occurs:

- The event resolves.
- The event stabilizes.
- The event returns to baseline, if a baseline value/status is available.
- The event can be attributed to etiology other than the study drug or to factors unrelated to study conduct.
- It becomes unlikely that any additional information can be obtained (participant or health care practitioner refusal to provide additional information, lost to follow-up after demonstration of due diligence with follow-up efforts).

Any event requiring hospitalization (or prolongation of hospitalization) that occurs during the course of a participant's participation in a study must be reported as a SAE, except hospitalizations for the following:

- Hospitalizations not intended to treat an acute illness or adverse event (e.g., social reasons such as pending placement in long-term facility).

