3 Perform the **End of Study Visit** (Visit 10, Day 42, of Part 1 and Visit 11, Day 77 of Part 2) unless participant discontinues study earlier than Day 63, then conduct End of Study Visit 30 days after last dose of study drug.

- 4 **MGD014 Infusion:** MGD014 will be administered by staff competent in antibody infusion; the PI (or designee) or a licensed physician assistant (PA), nurse practitioner (NP) or Research Nurse. A research assistant (RA) may obtain and record vital signs and provide other participant care necessary during the MGD014 infusion.
- Part 1: The first participants of each dose cohort are monitored for 24 hours on site following infusion; subsequent participants at the same dose level will be monitored for 12 hours on site following infusion.
- Part 2: Participants are monitored for 6 hours on site following their first infusion. Participants will be monitored for 4 hours on site following subsequent infusions.
- 5 **Participant identifier (PID) assignment:** This is a computer generated 5-digit number assigned to each participant after the informed consent is signed.
- 6 **Study-specific identifier (SID) assignment:** This is a sequential study specific number assigned to each participant at enrollment.
- 7 **Dose Cohort Assignment:** Part 1 only: This assignment occurs at the time of infusion and determined by the prior participant's safety data collected during their 2-week DLT period following the dose.
- 8 **Medical History:** Medical history obtained at screening will include demographic information (date of birth, gender, race, ethnicity), participant's medical history, and HIV medication history, and (CD4 nadir and peak HIV-1 viral load, if available).
- 9 **Physical Exam:** Includes a complete review of systems, and vital signs. Obtain the weight at screening, and prior to the dose of MGD014 at each infusion.
- 10 **Vital Signs:**
- Screening visit: T, P, BP, and RR and includes height and weight measurements.
 - Infusion Visits: vital signs include T, P, BP, and RR. The weight is only taken upon arrival at the clinic. Vital signs are taken before infusion (approximately 10 minutes before the infusion); at 15, 30, and 60 minutes after the start of infusion; at end of infusion; then every 15 minutes up to and including 60 minutes, then every 60 minutes up to 6 hours after the completion of first infusion and up to 4 hours for subsequent infusions after the completion of infusion. Vital signs have a +/- 5-minute window.

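### Protocol 9.10 can end a fully dosed Part 2 participant's study over a harmful repeat of the optional post-treatment leukapheresis, moving the last visit from Day 77 to about Day 58

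*Protocol*

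**What the plan says.** Leukapheresis is optional in both parts. A Part 2 participant who consents has one at baseline and one after treatment. Protocol 4.3 places the latter in Step 3: "a second and final leukapheresis procedure is completed 2 weeks (+/- 2 weeks) following the final MGD014 infusion". Protocol 14.5.1 and SAP 4.9.1 give the same timing as Day 42 ± 2 weeks.

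Under Protocol 9.10, a Grade 3 or higher toxicity during the procedure is reviewed case by case. The procedure may be repeated if the cause was situational and harmless. If instead the investigator, the apheresis medical director or the medical monitor determines "that repeated leukapheresis would be harmful to the participant, then he/she will be terminated from the study", that is the outcome. The following paragraph exempts only raised blood pressure, and it makes clear that study participation is at issue, not just the procedure.

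Appendix 1 footnote 3 sets the Part 2 End of Study Visit at Day 77, "unless participant discontinues study earlier than Day 63, then conduct End of Study Visit 30 days after last dose of study drug".

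Three other provisions bear on this:
- Section 5.3, on stopping infusions (a DLT included): "All participants who discontinue treatments should comply with protocol specified visits and follow-up as required by the protocol".
- Section 5.3.2 lists reasons for ending a participant's follow-up. Harm from leukapheresis is not among them.
- Section 4.5 describes a "post treatment period of 6 weeks following the final MGD014 infusion through end of study, which is approximately 5 times the anticipated 8-day half-life".

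**The concern.** The rule makes sense at baseline, before any drug is given, when a second procedure still lies ahead. At the second Part 2 procedure all three infusions have been given and no further leukapheresis is scheduled. Declining to repeat it would remove the procedural risk, so ending study participation adds no clear protection. It does set off the early End of Study Visit.

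The result is also out of line with the rest of the protocol. A participant whose infusions stop for a drug DLT stays on the protocol visits, while one who reacts to an optional collection procedure after full dosing does not.

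At stake is late follow-up in the only multi-dose cohort, which has up to 6 participants. Immunogenicity is a secondary objective, and Appendix 2 schedules one ADA sample after the third dose, at Day 77. In the monkey study (Protocol 2.2.2), 6 of the 10 ADA-positive animals were first positive in the recovery period, between Days 50 and 91. Late ADA is therefore a documented possibility, although the protocol does not say how many of the 6 appeared more than 30 days after the last dose.

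**Working it through.** **Inputs.** Last dose Day 28 (4.3 Step 3, Appendix 1). Second leukapheresis 14 ± 14 days later (4.3, 9.10). Planned End of Study Visit Day 77; early visit at last dose + 30 days if the study is discontinued before Day 63 (Appendix 1 footnote 3). Anticipated half-life 8 days (4.5).

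**The plan's own figures.** 28 + 14 = Day 42, as in 14.5.1. 77 / 7 = Week 11, as in Appendix 1. Six weeks is 42 days, and 42 / 8 = 5.25 half-lives, which agrees with the approximate 5 in Section 4.5.

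**Timing.** The second leukapheresis falls between 28 + 14 − 14 = Day 28 and 28 + 14 + 14 = Day 56 (Day 57 at most with the +1 day infusion window). That is always before Day 63. The early End of Study Visit is at 28 + 30 = Day 58 (Day 57 to 59 with the ±1 day infusion window).

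**Follow-up after the last dose.** Appendix 1 and Section 4.5 imply different planned lengths, so both are shown. The last column assumes one-phase exponential decline, 2^(−days/8).

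| Last visit | Days after last dose | Half-lives | Drug remaining |
|---|---|---|---|
| Day 77 (Appendix 1) | 77 − 28 = 49 | 49/8 = 6.1 | 1.4% |
| 6 weeks (Section 4.5) | 42 | 42/8 = 5.25 | 2.6% |
| Day 58 (early) | 30 | 30/8 = 3.75 | 7.4% |

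Loss against Appendix 1: 49 − 30 = 19 days, 19/49 = 38.8%. Loss against Section 4.5: 42 − 30 = 12 days, 12/42 = 28.6%.

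**Visits lost**, taking termination as immediate:
- event on Day 49 to 56: Day 63;
- event on Day 42 to 48: Days 49 and 63;
- event on Day 28 to 41: Days 42, 49 and 63.

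**Samples.** The final ADA, PK, RO and safety laboratory samples move from Day 77 to Day 58, which is 19 days earlier. In the schedule table as it can be read, chemistry panels after the third-infusion visit go from two (Days 63 and 77) to one (Day 58).

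**Adverse event window.** Section 12.2.1 says adverse events "will be evaluated from the time a signed and dated ICF is obtained until 30 days following the last dose of study drug". For Part 2 that is 28 + 30 = Day 58, the same day as the early visit.

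**The case against.** The strongest reply is that 9.10 hardly reaches this case. Its test is whether a repeat would be harmful, and nothing is scheduled after the second procedure. The rule fires only if someone proposes an unscheduled repeat, for example because the collection was stopped early. If enough cells were collected before the event, nobody need ask. That stands as a limit. A reader might infer that any Grade 3 event at the second leukapheresis ends follow-up; the text does not say so.

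A reader might also infer that adverse event data for the primary objective are lost. The documents do not establish this. Section 12.2.1 stops routine evaluation at Day 58 anyway, and after 30 days Section 12.2.3 says "only SAEs the PI (or designee) considers related to study drug or a protocol procedure, should be reported to the sponsor". Existing adverse events must be followed until resolved, chronic or stable (12.2.6), and SAEs unresolved when participation ends are also followed (12.2.3). Section 12 does run to the later of the End of Treatment Visit and 30 days, and Appendix 1 schedules adverse event assessment at Days 63 and 77. Loss of new non-serious events is therefore possible but not shown.

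Nor does the participant leave unexamined. An End of Study Visit with safety labs, ADA, PK and RO still takes place, five days before the dropped Day 63 visit. Section 5.3.1 may allow replacement, although it speaks of participants who withdraw rather than those terminated. Replacement would not restore this participant's follow-up.

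The event is also remote. The documents give no rate. Assuming a Grade 3 or higher non-blood-pressure risk per procedure of 0.1%, 1% or 5%, and all six consenting, the chance of at least one such event at the second procedure is 1 − (1 − p)^6 = 0.6%, 5.9% or 26%. The further conditions, a proposed repeat and a finding of harm, reduce it again.

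The protocol does not state the reason for the rule, and the apheresis SOP it cites is not available, so it would go too far to say that termination has no protective purpose. The remaining visits do include blood draws.

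**Conclusion.** The point holds as a narrow drafting fault with a cheap remedy. After a qualifying event, 9.10 offers repeat or terminate; it has no branch for skipping the repeat and staying in follow-up. For a fully dosed Part 2 participant, termination cuts follow-up after the last dose by 19 days against Appendix 1, or by 12 days against Section 4.5, and leaves it at 3.75 half-lives, short of the 6 weeks the protocol sets for itself.

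At most 6 participants plus any replacements are exposed, and only those who consent to the procedure. No planned analysis changes apart from the post-treatment QVOA value, which is missing whether or not the participant stays.

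The conclusion assumes that the third infusion is given on Day 28, that an unscheduled repeat is considered and judged harmful, and that the decision takes effect by about Day 58. A decision on Day 59 to 62 would come too late for a Day 58 visit, and one on or after Day 63 would leave the visit at Day 77. Events at leukapheresis before dosing, in Part 1 or at Part 2 baseline, cost no post-dose follow-up in that part and lie outside the point.

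**What to change.** In Protocol 9.10, for the post-treatment Part 2 leukapheresis only, replace termination with: *no further leukapheresis will be performed (QVOA treated as missing) and the participant continues scheduled safety, laboratory, PK and ADA follow-up through Day 77.* Leave the handling of pre-dose leukapheresis events unchanged.

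This is one sentence and adds no visits to the existing schedule. The downside is that the participant keeps the visits and blood draws already planned, which he or she may still decline.
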